4.2 Handling of dropouts or missing data

Analysis is based on observed case only.

If the Baseline value is missing, the Screening value may be used as the Baseline. In general, if no measurement is available prior to receiving study medication, then the Baseline value is treated as missing, and will not be imputed.

Premature withdrawal visits should be assigned to what would have been the next scheduled visit for the particular assessment that is being summarized. If a premature withdrawal visit occurs on the same date as a scheduled visit, then the assessments will be summarized with the scheduled visit.

Safety variables

For analyses of AEs and concomitant medication usage, a complete date must be established in order to correctly identify the AE or medication as occurring during treatment or not. For purposes of imputing missing components of partially-reported start and stop dates for AEs and for medication use, the algorithms listed below will be followed. Start and stop dates of AEs or concomitant medication will be displayed as reported in the subject data listings (i.e., no imputed values will be displayed in data listings).

- Missing start day, but month and year present: If the start of study medication occurred in the same month and year as the occurrence of the AE/concomitant medication, the start day of the event/concomitant medication will be assigned to the day of first intake of study medication. Otherwise the start day will be set to the 1st day of the month.
- Missing start day and month, but year present: If the start of study medication occurred in the same year as the occurrence of the AE/concomitant medication, the start day and month will be assigned to the date of first intake of study medication. Otherwise the start day and month will be set to January 1st.
- If start day, month, and year are missing, start date will be replaced by the date of first study drug administration or by the first day of January of the year of the end date, if the first administration date is after the end date.
- Missing end day, but month and year present: The end day will be set to the last day of the month.

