6.4 Prior and concomitant medications

Prior medications include any medications that started prior to the start date of study medication. Past medications are a subset of prior medications and include prior medications with a stop date before the date of first study medication administration.

Concomitant medications will be assigned to the treatment period according to whether they were taken at least one day in common with the study medication in that period. That is, if the start or end date of the concomitant medication is on or between the first study drug administration date and the last study drug administration date plus 14 days, or, if the concomitant medication starts prior to first study drug administration and ends after the last study drug administration date plus 14 days.

Concomitant medications will be assigned to the follow-up period if the start date of the concomitant medication is after the last study drug administration date plus 14 days.

A medication can be defined as both prior and concomitant. Where a medication start or stop date is (partially) missing, the medication will be considered a concomitant medication, unless the partial data is suggesting otherwise. Imputation of dates will follow the rules described in section [Section 4.2](#). Concomitant medications will be summarized for subjects in the SS. The following information will be included in the listings: reported term, dose per intake and dose unit, frequency, formulation, route, indication, start and stop dates (including relative study day), and in case of missing stop date, the information whether the intake of medication is ongoing.

Past medication summaries will be generated for disease-modifying antirheumatic drugs (DMARDs), non-steroidal anti-inflammatory drugs (NSAIDs), and anti-tumor necrosis factors (anti-TNFs) by anatomical therapeutic chemical (ATC) Anatomical Main Group (ATC Level 1), Pharmacological Subgroup (ATC level 3), and PT).

Concomitant DMARDs and NSAIDs will be summarized by WHO-DD Anatomical Main Group (ATC Level 1), Pharmacological Subgroup (ATC level 3), and PT). Concomitant medications other than DMARDs and NSAIDs will also be summarized.

Intake of any new prohibited medication since last visit is collected and presented in a separate listing.

7

MEASUREMENTS OF TREATMENT COMPLIANCE

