10.2 Adverse events

Adverse events with start date prior to first administration of study medication are defined as pre-treatment AEs. No summaries of these events will be produced although they will be included in listings.

Adverse events that started more than 70 days after the last administration of study medication are defined as post-treatment AEs. Such events will not be included in tabulated summaries, but will be listed.

Treatment emergent AEs are all AEs starting on or after the date of first study medication and up to 70 days after the last (most recent) dose of study medication. AEs occurring more than 70 days after the last (most recent) dose will not be considered treatment emergent, regardless of whether this occurs during the safety follow-up period, or after a treatment gap of more than 70 days.

If a start date is missing, then the AE will be considered a treatment emergent adverse event (TEAE). Duration should not be calculated if there is missing stop date information.

If the intensity of an adverse event is unknown, it is considered as severe. If the relationship to study drug is missing, it is considered as related.

Tables showing TEAEs, serious TEAEs, non-serious TEAEs, TEAEs leading to discontinuation of study drug, TEAEs by maximum intensity, TEAEs by relationship, serious TEAEs by relationship, fatal TEAEs by relationship, TEAEs including subject numbers will be provided on the SS.

Additionally, more detailed summaries of TEAEs will be presented, which include the exposure adjusted incidence rate (EAIR) with associated 95% confidence interval, and the exposure adjusted event rate (EAER).

The EAIR is defined as the number of subjects (n) with a specific AE adjusted for the exposure and will be scaled to 100 patient-years:

$$EAIR = 100 \cdot n / \sum_{i=1}^N T_{Exp,i}$$

If a subject has multiple events, the time of exposure is calculated to the first occurrence of the AE of interest. If a subject has no events, the total time at risk is used.

Exact Poisson 95% confidence intervals for incidence rates are calculated using the relationship between the Poisson and the Chi-square distribution (Ulm, 1990):

$$LCL = \chi_{2n, \alpha/2}^2 / 2$$

$$UCL = \chi_{2(n+1), 1-\alpha/2}^2 / 2$$

where n is the number of subjects with a specific AE for the incidence rate of interest and is the basis for the number of the degrees of freedom for the chi-square quantile for the upper tail probability χ^2 .

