The EAER will be the number of AEs including repeat occurrences in individual subjects divided by the total time at risk scaled to 100 patient-years and calculated using:

$$EAER = 100 \cdot N_{AE} / \sum_{i=1}^N T_{Risk,i}$$

where N_{AE} is the total number of AEs.

No confidence interval will be computed for EAER.

Where an AE start date is (partially) missing, the AE will be considered TE if possible. Imputation rules provided in Section 4.2 are based on the assumption that if the start date is incomplete, either day only is missing, or day and months are missing, or date is completely missing. Although the algorithms for treatment-emergence depend on the onset date, imputation rules are provided for resolution date as well, as these may be needed for certain statistical analyses, such as an analyses of AE prevalence or AE duration.

Listings based on SS for all AEs will be provided. A glossary for the reported terms will also be generated utilizing SOC, HLT, and PT.

Anticipated SAEs, as described in Section 10.5 of the clinical study protocol, will not be summarized either by any additional tables or listings, as they are included in the standard AE summaries.

AEs of interest will be summarized. The following AEs of interest will be summarized in stand-alone tables:

- Opportunistic infections
- Malignant or unspecified tumors
- Malignant tumors
- Serious cardiovascular events
- Demyelinating-like disorders
- Aplastic anemia, pancytopenia, thrombocytopenia, neutropenia, and leucopenia
- Serious bleeding events

For the following AEs of interest, no additional tables will be provided, as these are included in the standard AE summaries:

- Serious infections
- Congestive heart failure
- Lupus and lupus-like illness
- Serious skin reactions (eg, Stevens Johnson Syndrome, toxic epidermal necrosis, and erythema multiforme)

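### SAP 4.2 moves a partly dated AE or drug start to first dose without checking the end date, so a record that ended before CZP can be counted as on treatment

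*SAP*

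**What the plan says.** SAP 4.2 (Safety variables) explains why AE and medication dates are imputed: "a complete date must be established in order to correctly identify the AE or medication as occurring during treatment or not". Three start-date rules follow.

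- **Day missing, month and year those of first dose:** "the start day of the event/concomitant medication will be assigned to the day of first intake of study medication". In any other month, the 1st of the month is used.
- **Day and month missing, year that of first dose:** "the start day and month will be assigned to the date of first intake of study medication". In any other year, 1 January is used.
- **Start completely missing:** first-dose date, replaced "by the first day of January of the year of the end date, if the first administration date is after the end date".

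Only the third rule refers to the end date.

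The classification rules stand elsewhere. SAP 10.2 states: "Treatment emergent AEs are all AEs starting on or after the date of first study medication", up to 70 days after the last dose. It adds: "Where an AE start date is (partially) missing, the AE will be considered TE if possible". It also says that an AE with a missing start date counts as a TEAE.

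SAP 6.4 calls a medication prior if it started before study medication, and then: "Past medications are a subset of prior medications and include prior medications with a stop date before the date of first study medication administration". A medication is assigned to the treatment period if it overlaps study medication by one day or more. In operational terms this is met, among other ways, "if the start or end date of the concomitant medication is on or between the first study drug administration date" and the last dose plus 14 days. The same section treats a drug with a partly missing date as concomitant except where the partial information points the other way. It refers the imputation itself back to SAP 4.2.

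**The concern.** The two partial-date rules can contradict a date that is already in the database. If the end is known and lies before first dose, the start cannot be the first-dose date, yet that is what the rules assign. The rule beside them avoids this error, so a record with no start information is dated more plausibly than one whose start year is known.

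Two outputs are at stake. TEAEs are the secondary safety variable (Protocol 4.2.1, SAP 2.2.2.1), and an AE that resolved during Screening could be tabulated as arising on CZP. The past DMARD, NSAID and anti-TNF summaries in SAP 6.4 could lose a drug that was stopped before CZP, and that drug could appear as concomitant instead.

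**Working it through.** The plan states no figure that depends on these rules, so the check is to apply them to example records.

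**Inputs.** D1 is the first-dose date, E the recorded end and S the imputed start. The rules come from SAP 4.2, 6.4 and 10.2. D1 = 20 June 2018 and the records are illustrative assumptions.

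**Rules in symbols.**

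- Day missing: S = D1 if month and year match D1, otherwise the 1st of the known month.
- Day and month missing: S = D1 if the year matches D1, otherwise 1 January of the known year.
- All missing: S = D1, but 1 January of the year of E if D1 is after E.
- TEAE by date: D1 ≤ S ≤ last dose + 70 days.
- Prior: S < D1. Past: S < D1 and E < D1.
- Concomitant: S or E lies between D1 and last dose + 14 days, or S < D1 and E is later than last dose + 14 days.
- Duration: E − S + 1, used here only to show date order.

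**Results with the rules as written.**

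| Record | Imputed S | Duration (days) | Class by the date rules |
|---|---|---|---|
| AE, start Jun 2018, end 12 Jun 2018 | 20 Jun 2018 | 12 − 20 + 1 = −7 | TEAE |
| AE, start 2018, end 5 Jun 2018 | 20 Jun 2018 | 5 − 20 + 1 = −14 | TEAE |
| AE, start missing, end 5 Jun 2018 | 1 Jan 2018 | 156 | pre-treatment |
| AE, start May 2018, end 5 Jun 2018 | 1 May 2018 | 36 | pre-treatment |
| Drug, start 2018, end 15 Mar 2018 | 20 Jun 2018 | −97 + 1 = −96 | concomitant; neither prior nor past |
| Drug, start 2017, end 15 Mar 2018 | 1 Jan 2017 | 439 | prior and past |

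Rows 1, 2 and 5 have a start after their own end. Rows 2 and 3 differ only in that row 2 has a known start year, and that extra fact produces the impossible date. Rows 4 and 6 show the limit of the problem: if the partial start falls outside the first-dose month (day missing) or year (day and month missing), the result is right.

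**Results with an end-date check in the first two rules.** Row 1: S = 1 June 2018, not a TEAE. Row 2: S = 1 January 2018, or the consent date if later, not a TEAE. Row 5: S = 1 January 2018, prior and past, not concomitant. The other rows do not change.

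**Reach for AEs.** Protocol 10.1.1 collects AEs from consent, so only Screening AEs can be affected. Screening lasts 1 to 5 weeks, or up to 12 weeks with LTBI prophylaxis. Assume a first-dose day uniform over the year and an onset uniform over the look-back:

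| Look-back (days) | Onset in first-dose month | Onset in first-dose year |
|---|---|---|
| 7 | 87% | 99% |
| 35 | 42% | 95% |
| 84 | 18% | 88% |

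These are shares of pre-dose onsets that fall where the rules could act. They are not shares of all AEs. A record must also have an incomplete start and a known end before first dose, and the documents do not say how often that occurs.

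**The case against.** The strongest reply is that SAP 4.2 only supplies dates and the classification sections give the right answer. For drugs, SAP 6.4 has an exception where partial information points the other way, and it requires a shared day with study medication. A recorded stop before first dose meets the exception and fails the overlap. For AEs, an event known to have ended before first dose cannot be treatment emergent, so the words in "Where an AE start date is (partially) missing, the AE will be considered TE if possible" can be read as excluding it. SAP 10.2 also counts an AE with a missing start as a TEAE, and SAP 3.2.1 assigns AEs starting on the Baseline visit to the Treatment Period. Both suggest a deliberately conservative policy, under which an error over-counts TEAEs and hides none. Listings show dates as reported, so the true stop date stays visible.

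Much of this stands, and it limits the point. A reader might infer that every affected drug is bound to be misclassified. The documents do not support that, because SAP 6.4 contains wording that would keep the drug out. Nor does the reply settle the matter. SAP 6.4 sends imputation back to SAP 4.2, and its operational test is met by the imputed start. SAP 10.2 does not define what is possible; it then refers to the SAP 4.2 rules and says that treatment emergence turns on the onset date. A conservative policy does not explain why the third rule checks the end date and the other two do not. Listings without imputed dates would disagree with the tables and show no reason for it.

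The missing-start sentence in SAP 10.2 has a further effect. A reader might infer that the better-documented AE is always classed worse. That holds for the imputed date, but not necessarily for TEAE status, since this sentence can also make the undated AE a TEAE.

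**Conclusion.** The point holds as an internal inconsistency with a definite dating error. For every AE or drug with a partial start in the first-dose month (day missing) or year (day and month missing) and a known end before first dose, SAP 4.2 gives a start after the end. Whether the record is then misclassified depends on which sentence the programmer follows. The risk is clearer for AEs, where the definition uses the start date alone, than for drugs.

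The number of such records cannot be derived from the documents. AE exposure is limited to Screening. The primary AU flare analysis has its own date rules in SAP 4.2 and is not affected, and the medication tables are descriptive. The change is worth making because the rule as stated gives a wrong date and the correction is nearly free.

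Three stronger readings are not supported:

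- **A washed-out biological would look like prohibited use.** SAP 6.4 takes prohibited intake from separately collected data shown in its own listing, not from imputed starts.
- **Every subject has at least two past NSAIDs exposed to the rule.** Inclusion criterion 9 requires intolerance or inadequate response to at least 2 NSAIDs, not that they were stopped. Stable NSAID use may continue (Protocol Table 6–1 and 7.8.1).
- **The past-medication tables describe treatment during the historical flare period.** SAP 6.4 does not tie them to that window.

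**What to change.** In SAP 4.2, add one condition to both partial-date rules. The first-dose date is used only if the end date is missing or falls on or after first dose. Otherwise the start is the 1st of the known month (day missing) or 1 January of the known year (day and month missing), and for an AE not before informed consent.

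Then align the two classification sections:

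- **SAP 6.4:** state that a drug with a known stop before first dose is past and not concomitant, whatever its imputed start.
- **SAP 10.2:** state that a partly or completely missing start makes an AE treatment emergent unless its known end is before first dose. This also reconciles the missing-start sentence with the third rule of SAP 4.2.

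The cost is one added sentence in SAP 4.2, a line of code per rule and short edits to SAP 6.4 and 10.2. No new data are needed. A programmed check for any imputed start later than the recorded end would show how many records are concerned.

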8 STUDY PROCEDURES BY VISIT

Section 5.2 (Schedule of assessment) letailed listing of 5-digit number assigned at Screening that serves as the subject identifier throughout the

detailed listing of procedures to be undertaken at each visit is described below. During the study, the Investigator will assess each subject over the entire study period of up to 109 weeks including a FU Period of 10 weeks after the last dose of the study drug. For Week 2 to Week 96 the visit window is ± 3 days from the actual date in Weeks from the initial administration of IMP (Week 0). For the FU Visit a window of 1-2 weeks is acceptable.

Visit 1 (Week -5 to -1) Screening 8.1

Prior to any study activities, subjects will be asked to read and sign an informed consent form (ICF) for participation in the study. All ICFs will have been approved by an IEC/IRB and will comply with regulatory requirements. Subjects will be given adequate time to consider any information concerning the study given to them by the Investigator or designee. As part of the informed consent procedure, subjects will be given the opportunity to ask the Investigator any questions regarding potential risks and benefits of participation in the study.

Assessments at the Screening Visit include:

- Confirm informed consent
- Review inclusion/exclusion criteria
- Demographic data (includes date of birth, gender, race/ethnicity)
- Washout of excluded medications (3 months for TNFs)
- Significant past medical and procedure history (including tobacco use) and concomitant disease (including axSpA history)
- Prior and concomitant medication
- Review of the uveitis history containing all documented UA
- Vital signs (pulse rate, systolic and diastolic blood pressures, and temperature)
- Physical examination (including weight) and extra-articular assessment (including the number of IBD exacerbations and number of psoriasis exacerbations [in subjects with concurrent psoriasis])

- Hematology, biochemistry, and urinalysis for clinical laboratory values
- Hepatitis-associated disease markers assessment:
 - Hepatitis B core antibody (HBc-Ab)
 - Hepatitis B surface antigen (HBs-Ag)
 - Hepatitis B surface antibody (HBs-Ab)
 - Hepatitis C virus antibody (HCV-Ab)
- Testing of antibodies to HIV
- Testing for HLA-B27 if unknown at Screening Visit
- CRP testing
- Serum pregnancy testing for women of childbearing potential
- TB evaluation

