- Missing end day and month, but year present: If the maximum of the subject's date of study termination or the date equivalent to 70 days after the subject's last intake of study medication is the same year as the occurrence of the AE/Concomitant medication, then the end day and month will be set to the maximum of the date of study termination or the date equivalent to 70 days after last intake of study medication. Otherwise the end day will be set to December 31st of the given year.

Efficacy variables

The start and end dates of flares will be imputed for the analyses of AU flares data, in order to allow the calculation of time intervals between 2 consecutive flares and the duration of flares. Different rules will be applied for pre-study and on-study period flares.

For the interim analysis, the pre-study period is starting 48 weeks prior to Baseline, i.e. 336 days prior to Baseline until Baseline. The on-study period for the interim analysis is starting from Baseline until week 48, i.e. until study day 336.

For the final analysis, the pre-study period is starting 24 months prior to Baseline, i.e. 730 days prior to Baseline until Baseline. The on-study period for the final analysis is starting from Baseline until week 96, i.e. until the date of the Week 96 or discontinuation visit. In addition, sensitivity and supportive analyses use different definitions (as defined in Section 8.1.2).

Pre-study period:

- Missing start day, but month and year present: Impute the first day of the month unless one of the following conditions apply:
 - Month and year are the same as month and year of the start date of pre-study period, then impute with the start date of pre-study period.
 - Month and year are the same as month and year of the end date of previous flare in the same eye, and the end date is clearly greater than end date of previous flare, then impute with the end date of previous flare.
 - In the case that month and year of the start date of pre-study period is the same month and year of the end date of previous flare in the same eye, then use the latest date of both for imputation.
- Missing start day and month, but year present: Impute January 1st unless one of the following conditions apply:
 - Year is the same as year of the start date of pre-study period, then impute with the start date of pre-study period.
 - Year is the same as year of the end date of previous flare in the same eye, then impute with the end date of previous flare.

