 - In the case that year of the start date of pre-study period is the same year of the end date of previous flare in the same eye, then use the latest date of both for imputation.
- Completely missing start dates of flares will only be imputed if it is clear based on the end date that the flare occurred within the pre-study period. Then the maximum (latest) of start date of pre-study period and end date of previous flare will be considered.
- Missing end day, but month and year present: Impute the last day of the month unless one of the following conditions apply:
 - Month and year are the same as month and year of the end date of pre-study period, then impute with the end date of pre-study period.
 - Month and year are the same as month and year of the start date of subsequent pre-study flare in the same eye before Baseline, then impute with the start date of subsequent pre-study flare.
 - In the case that month and year of the end date of pre-study period is the same month and year of the start date of subsequent pre-study flare in the same eye, then use the earliest date of both for imputation.
- Missing end day and month, but year present: Impute December 31st unless one of the following conditions apply:

- Year is the same as year of the end date of pre-study period, then impute with the end date of pre-study period.
- Year is the same as year of the start date of subsequent pre-study flare in the same eye, then impute with the start date of subsequent pre-study flare.
- In the case that year of the end date of pre-study period is the same year of the start date of subsequent pre-study flare in the same eye, then use the earliest date of both for imputation.
- Completely missing end dates of flares will only be imputed if it is clear based on the start date that the flare occurred within the pre-study period (of 2 years prior to baseline). Then the minimum (earliest) of end date of pre-study period (i.e. the day prior to treatment start date), the day prior to start date of subsequent pre-study flare in the same eye, or the start date plus the median duration of flare in that subject will be considered. The median duration of flare is determined from all flares recorded for that subject that have complete start and end dates (regardless of eye), including any flares prior to or during the pre-study period and on-study period.

On-study period (Baseline until end of treatment):

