8.1.1 Derivations of primary efficacy variable

The primary efficacy variable is the number of distinct episodes of AU flares in the Treatment Period. Per protocol, a flare is considered a new episode if a gap of at least 3 months occurs between 2 flares. If AU flare episodes as reported by the investigator occur less than 3 months

(90 days) apart in the same eye, these will be programmatically corrected, such that a new AU flare within 3 months (90 days) after the end of the previous AU flare in the same eye will be considered as pertaining to the same AU episode. These flares will then be counted as one episode. Otherwise, if the time interval between 2 consecutive AU flares is greater than 3 months (90 days), or a separate eye is affected, the AU flares will be considered as separate episodes.

Pre-study and on-study AU flare episodes will be counted. An episode of AU flares is considered as pre-study, if the start date of flare is before the start date of study medication and if start date of flare occurs within the 24 months (730 days) prior to the start of study medication. For the interim analysis, an episode of AU flares is considered as pre-study if the flare occurs within 48 weeks (336 days) prior to the start of study medication.

For the Week 96 (primary) analysis, an episode of AU flares is considered on-study, if the start date of flare is on or after the start date of study medication and the start date of the flare occurs up to and including the last visit in the treatment period, i.e. Week 96 or discontinuation visit.

Pre-study and on-study flares of the same eye will be combined if the time interval between the end of pre-study flare and the start of subsequent on-study flare is less than 3 months (90 days). The resulting flare episode will be considered as pre-study flare episode.

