The log-time offset in the Poisson model will consist of the length of pre-study and on-study reporting periods in days. As the documentation of pre-study episodes is extended to up to 2 years prior to Baseline, the pre-study period length for offset is 730 days for each subject, unless the date of first uveitis flare is within 2 years of baseline, in which case the pre-study period length will be from date of first uveitis flare until baseline. The on-study period length for offset is the time in days from start of study medication until last visit, i.e. Week 96 or discontinuation visit. For the interim analysis, an offset of 336 days will be used for the pre-study period or time since first uveitis flare if shorter than 336 days, and the time in days from start of study medication until week 48 visit (taken as 336 days) or early termination visit (taken as 14 days after the last treatment) where applicable will be used for the on-study period.

Disease duration of axSpA, which will be included in the Poisson model as a factor, is calculated as defined in Section 6.2, and is categorized into <2 years and ≥ 2 years.

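### The pre-study start-date rule in SAP 4.2 can only add flares at the opening of the historical window, which favours CZP by an amount the documents leave unknown

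*SAP*

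**What the plan says.** - **Year-only onset.** For pre-study flares SAP 4.2 defaults to 1 January, with an exception for the year in which the window opens: "Year is the same as year of the start date of pre-study period, then impute with the start date of pre-study period".
- **Month-only onset.** The default is the first of the month, with the matching exception: "Month and year are the same as month and year of the start date of pre-study period, then impute with the start date".
- **Earlier same-eye flare.** Where the opening year "is the same year of the end date of previous flare in the same eye, then use the latest date of both for imputation". Either way, the assigned date is never before the window.
- **Fully missing onset.** "Completely missing start dates of flares will only be imputed if it is clear based on the end date" that the flare lay in the period. Partial onsets carry no such condition.
- **Counting.** SAP 8.1.1 takes an episode that began before first dose as pre-study "if start date of flare occurs within the 24 months (730 days) prior to the start of study medication".
- **Time.** "the pre-study period length for offset is 730 days for each subject", shorter only when the first-ever flare falls within two years of Baseline.
- **Other windows.** SAP 8.1.2 repeats the model with 672-, 365- and 336-day windows, and the interim uses 336 days. The only date-quality analysis in 8.1.2 concerns fully missing end dates.
- **What is recorded.** Protocol 8.1 lists at Screening "Review of the uveitis history containing all documented UA", and SAP 4.2 computes a subject's median flare duration from complete flares "including any flares prior to or during the pre-study period and on-study period". Against this, SAP 8.1.1 describes documentation reaching back no more than two years, and SAP 4.3 ties flare collection to 48 or 96 weeks.

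**The concern.** In this single-arm study the historical count is the whole comparator, and whether a flare enters it depends only on its start date. The general default (1 January, or the first of the month) would usually place an ambiguous flare before the window. The exception moves it inside while the offset stays the same. Events are added without time, so the CZP/historical ratio falls with no drug effect.

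Retrospective onsets are the ones most likely to be partial. On-study flares are asked about at every visit and confirmed with an ophthalmologist (Protocol 9.1.1). No planned analysis would reveal the effect: the repeats with other windows re-date ambiguous flares to whichever window start applies, if the rule is applied afresh to each window, as SAP 4.2 reads.

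**Working it through.** **1. The plan's own figure.** The documents give no figure for this rule. The rates used below come from SAP 2.4 (29.2 per 100 subject-years before CZP, 14.6 on CZP) and reproduce its sample size. With the Poisson-regression formula, N = (z_a√V0 + z_b√V1)² / (T·λ0·(ln RR)²), V0 = 4, V1 = 2 + 2/0.5 = 6, T = 1.5, λ0 = 0.292 and two-sided alpha 0.049, N is 171.0 in total, so 85.5 or 86 per group; power at 86 is 80.2%.

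**2. What the text does to one flare.** First dose 1 July 2018, so the window opens 1 July 2016. A flare has onset recorded as 2016 and a known end of 10 March 2016. SAP 4.2 gives it a start of 1 July 2016 and SAP 8.1.1 counts it. Its start is now 113 days after its end, and the duration formula in SAP 8.3.1 returns −113 + 1 = −112 days.

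**3. The rule alone, closed form.** Assume a constant flare rate, window openings spread evenly over the calendar year, all older flares recorded, and no merging. On average half a year of the opening year precedes the window. With q the share of onsets that are year-only, the count is multiplied by 1 + 0.5q/L, where L is the window in years. The true 730-day count is 86 × 0.292 × 2 = 50.2, and the extra flares are 86 × 0.292 × 0.5 × q = 12.6q.

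| Year-only share q (assumed) | 10% | 25% | 50% |
|---|---|---|---|
| Extra flares, 730 days | 1.3 | 3.1 | 6.3 |
| Inflation, 730 days (0.25q) | 2.5% | 6.25% | 12.5% |
| Historical rate per 100 subject-years | 29.9 | 31.0 | 32.9 |
| True ratio 1 reads | 0.976 | 0.941 | 0.889 |
| True ratio 0.50 reads | 0.488 | 0.471 | 0.444 |
| Inflation, 365 days (0.5q) | 5% | 12.5% | 25% |

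For month-only onsets the factor is 1 + (0.5/12)q/2 = 1 + 0.021q: 0.5% at q = 25% and 2.1% even at q = 100%.

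**4. If sites recorded only two years.** The 730-day window then has no older flares to pull in. The 365-day row is unchanged, because the opening year reaches at most 365 + 365 = 730 days back; the 336-day window reaches 336 + 365 = 701 days. For the 672-day window only 730 − 672 = 58 days of older records exist. With a = 58/365 = 0.159, the mean exposed time is a − a²/2 = 0.146 years, and 0.146/1.84 = 0.079, so inflation is 0.8, 2.0 or 4.0% at q = 10, 25 or 50%.

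**5. Net of the SAP's other rules, 730 days.** A simulation applied SAP 4.2 and 8.1.1 with 90-day same-eye merging. It assumed two eyes, flares of 20 to 70 days, gamma-varying rates and six years of recorded history.

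| Historical count | q = 10% | 25% | 50% |
|---|---|---|---|
| Against ambiguous flares correctly placed, end dates known | 1.025 | 1.06 | 1.13 |
| Net against truth, end dates known | +1.5% | +3.7% | +7.0% |
| Net against truth, end dates also year-only | +0.3% | +0.7% | +0.9% |

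The net figures are smaller because 31 December end dates and merging remove other episodes. At a true ratio of 1, false positives in CZP's favour were 2.2% with full dates and 2.8, 4.3 and 6.3% at q = 10, 25 and 50% with end dates known (600 runs, Monte Carlo error up to about 1 point). The first step is within that error.

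**The case against.** The strongest point is about the dataset. If sites recorded only the two-year lookback, a flare entered under the opening year is already stated to lie inside it; the rule merely supplies its earliest possible date, and 1 January would wrongly drop it. Inflation of the primary count would then be about zero. The documents are mixed, so this stands as a limit on the primary analysis. It does not protect the 365- and 336-day analyses.

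The SAP's own end-date and merging rules offset part or nearly all of the excess. This also stands, but the offset is accidental and depends on how end dates were recorded. Month-only dates matter little, and Screening may be extended to five weeks to obtain ophthalmologist information, which should limit year-only dates.

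Two textual points also stand. Where an earlier same-eye flare ended later in the opening year, that later date is used; such a flare follows one that ended inside the window, so it cannot predate it. And a flare moved to within 90 days of a same-eye flare that ended before the window is merged with it and may not be counted.

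The on-study rule mirrors this one, dating partial onsets in the month or year of first dose to first dose. With prospective collection it is a weak counterweight.

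A reader might infer that the primary rate ratio is overstated by the full closed-form amount, or that every flare of this kind is miscounted. The documents do not support either: they leave open whether older flares are held, give no share of partial dates, and contain the exception and offsetting rules above.

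**Conclusion.** The concern holds in a limited form. As written, the dating rule at the window's opening moves flares only inwards, lacks the safeguard that the same section applies to fully missing onsets, and is not covered by any sensitivity analysis. Its direction favours CZP.

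Its size cannot be fixed from the documents. The 730-day figures rest on assumed shares of year-only onset and on older flares being recorded; without those flares the primary analysis is essentially unaffected. The 365-day figures need only the two-year lookback and the rule being applied to each window, but they are for the rule alone and no net figure was computed. At small shares the rule would not overturn a true halving of the rate: 0.50 reads 0.488 at 10%.

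**What to change.** In SAP 4.2, pre-study start dates:

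- Do not move a partial start to the window's opening when a known end date or an adjacent same-eye flare places the flare before it. With end dates known, the end-date check alone cut the simulated excess over correct placement to 0.6, 1.5 and 3.0% at q = 10, 25 and 50%.
- Otherwise derive one date per flare, independent of any window: the midpoint of its feasible interval, bounded by the end date, adjacent same-eye flares and the actual collection lookback. Apply every window to that date. State what the lookback was.
- Report the number of flares whose place in a window depends on an imputed start. Add to SAP 8.1.2 a repeat of the primary model, and of the 672-, 365- and 336-day repeats, without them.

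The lookback bound matters. A fixed 1 July date is nearly unbiased if all older flares are recorded (simulated count within 0.3% of correct placement for q up to 50%). With only two years recorded, it would discard every such flare when the window opens after 1 July: 0.125 of 0.5 year on average, or 25% of genuine in-window flares of this kind. The bounded midpoint itself was not simulated.

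The cost is SAP wording, minor programming and a few extra model runs. The historical rate may come out slightly lower; N = 86 is unaffected.
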